5. STUDY DESIGN

This is a prospective non-randomised mechanistic study of 35 patients including a control group of 5 patients with SVT and 30 patients undergoing elective AF ablation.

The 30 patients undergoing AF ablation will include 10 who are undergoing elective AcQMap guided procedures in order to correlate non-contact propagation patterns with contact substrate mapping. These 10 patients will also undergo cardiac MRI before and after the ablation procedure.

The remaining 20 patients will also undergo electroanatomical voltage mapping using a contact force guided bipolar ablation catheter in order to compare the two methods/technologies. This is a non-blinded comparison study.

The 5 control patients will be undergoing elective catheter ablation procedures for left sided accessory pathways. Additional left atrial electroanatomical mapping will be performed to define normal electrophysiological properties for comparison.

Participants will be identified in clinic or after listing for the procedure. Screening and formal recruitment will then be undertaken, with the research study conducted during the ablation procedure. No follow up is required but participants undergoing AcQmap guided ablation and cardiac MRI will undergo a repeat cardiac MRI within 6 months following the procedure.

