20 patients undergoing AF ablation will have a further map completed using a contact force guided bipolar irrigated ablation catheter (Abbott Tacticath) during the same pacing protocol. For all voltage maps a minimum of 300 points should be obtained with full and equal covering of the atrial surface, interpolation should be set to 7mm, and set to only include points with contact force between 5 and 50grams.

Subgroup undergoing AcQMap guided mapping and ablation

10 patients with persistent AF who are undergoing AcQMap guided elective catheter ablation procedures will be included in this sub-study. All patients will undergo the same main study mapping procedure outlined above. In addition, AcQMap recordings will also be obtained. Recordings will be made during pacing with the same main study protocol and two 30 second recordings will be undertaken during AF. HD grid contact recordings will then also be obtained in regions of prominent rotational and irregular conduction identified by AcQMap and ablation performed at the operator's discretion.

For patients presenting in sinus rhythm or AF, all required mapping should be completed in the presenting rhythm followed by either AF induction (using incremental burst atrial pacing) or DCCV respectively before completion of mapping procedures. Ablation in line with standard clinical care will be undertaken following completion of all mapping procedures.

For an outline of study procedures versus standard care and estimated time requirements, please see appendix B.

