9.3. Analysis of Outcome Measures

Control group:

All electrogram samples will be analysed at baseline (long) cycle length and classified as normal or abnormal (see above definitions in section 4). The same sampling points will then be analysed at short cycle length and classified in the same way. The proportion of electrograms changing from normal to abnormal will be recorded as will the change in electrogram amplitude and duration.

The whole chamber mean, median and distribution of voltage amplitude at long cycle length will be analysed. This will also be done for each atrial segment. The segment with the lowest mean amplitude will be identified and the cut-off for the value representing the upper 95% of recordings in that segment calculated. This will be used as the value representing the lower limit of normal for subsequent study analyses.

All participants:

All electrogram samples will be analysed at baseline (long) cycle length and classified as normal or abnormal (see above definitions in section 4). The same sampling points will then be analysed at short cycle length and classified in the same way. The proportion of electrograms classified as normal and abnormal at each cycle length will be calculated for the full sample set and according to baseline electrogram amplitude (<0.5mV, 0.5-lower limit of normal, and >lower limit of normal)(lower limit of normal defined above from analysis of the control group).

For each participant, conduction velocities will be analysed in regions of different baseline electrogram amplitude at both long and short cycle length. This will be done using the Turbomap feature in Precision to create an activation map (specified as measuring on maximum negative dV/dt). Conduction velocity will be calculated as a mean of 5 measurements using the difference in activation times between 2 points in a straight line at set distance through the region of least isochronal crowding. This will be done in regions of low, intermediate and preserved voltage at long and short cycle length.

The outcome measures will be assessed in all patients in whom the study procedure was performed.

Voltage mapping subgroup:

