For all maps obtained in this subgroup using both the HD grid and ablation catheter, bipolar voltage amplitudes will be compared. Mean amplitudes will be compared for the entire chamber and each atrial segment (anterior, septal, inferior wall, posterior wall, roof, lateral wall). Each sampling point obtained using the ablation catheter in sinus rhythm/baseline pacing cycle length will then be compared to an equivalent nearest point obtained by the HD grid in sinus rhythm/baseline pacing cycle length to give a difference (+/-) in amplitude recorded. Mean differences will be compared for the whole atrium and each segment as outlined above.

The outcome measures will be assessed in all patients in whom the study procedure was performed.

AcQMap subgroup:

Qualitative and quantitative assessments of conduction patterns identified on AcQMap during AF will be made with regions of frequent focal firing, slow conduction, rotational activation or irregular activation identified (according to AcQTrack and visual interpretation of the operator in line with and according to

their prior experience). Contact electrograms using the HD grid will be recorded at these regions and classified according to their degree of fractionation. Regions identified as above by the operator will be compared to the rest of the atria according to sinus rhythm voltage amplitude and proportional change in electrogram morphology and conduction velocity with changing pacing cycle length.

The outcome measures will be assessed in all patients in whom the study procedure was performed.

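### No masking is specified for AcQMap region labelling or electrogram classification, so knowledge of region, cycle length or, in some patients, voltage may influence the labels

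*Combined protocol and SAP*

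**What the plan says.** **Region labels.** In Section 9.3 (AcQMap subgroup), areas of focal firing, slow conduction, rotational or irregular activation are identified "according to AcQTrack and visual interpretation of the operator", drawing on the operator's experience. No rule says how software output and visual reading are combined. The comparison follows directly: "Regions identified as above by the operator will be compared to the rest of the atria according to sinus rhythm voltage amplitude", and also on the change in morphology and conduction velocity with cycle length.

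**Contact recordings in AF.** Section 7.7 states that "HD grid contact recordings will then also be obtained in regions of prominent rotational and irregular conduction identified by AcQMap". Section 9.3 has these recordings "classified according to their degree of fractionation", without a scale or a named reader.

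**Electrogram classification.** Section 9.3 states that "All electrogram samples will be analysed at baseline (long) cycle length and classified as normal or abnormal". The same points are then read at short cycle length. Section 4 defines abnormal numerically: three or more deflections with a duration of 50 ms or more. The plan does not say whether software or a person counts deflections and measures duration.

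**Order of mapping.** The AcQMap paragraph of Section 7.7 says: "For patients presenting in sinus rhythm or AF, all required mapping should be completed in the presenting rhythm", with AF induction or cardioversion afterwards. The paragraph for all patients in the same section has anyone in AF cardioverted at the start and then mapped during pacing.

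**Data handling.** Section 10.2 provides for coded data on separate workstations. The coding hides patient identity. Nothing is said about hiding cycle length, voltage or region.

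**The concern.** Section 3 expects intermediate-voltage regions to coincide with slow and irregular propagation in AF, and Section 9.2 expects electrograms to become abnormal at the shorter cycle length. The people who make the labels work under those expectations, and the plan has no step that keeps the two sides of each comparison apart. If a borderline electrogram is called abnormal a little more often because it is known to be a short-coupled beat, or to lie in a flagged region, the planned comparison will show a difference that comes from the reading.

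The region comparison is a secondary objective in 10 patients. The cycle-length reading is wider, because it covers all 30 AF patients and the 5 controls. The lower limit of normal voltage in the primary objective is a recorded amplitude and does not depend on these readings. Section 3 presents the results as pilot data for larger multi-centre studies, so a reading artefact could be carried forward.

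**Working it through.** The plan states no error rate, effect size or significance level on this point, so there is no figure to reproduce. The check is to see what each reader could know, and then to illustrate how sensitive the tests would be.

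**1. What the reader could know at each step**

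| Step | Knowledge that the text implies | Masking described |
|---|---|---|
| AcQMap region labelling, paced map made first | Voltage map exists; viewing it is neither stated nor excluded | None |
| AcQMap region labelling, AF mapped first | No paced map yet | None needed against voltage |
| HD grid contact recordings and fractionation grade | Region already flagged | None |
| Normal/abnormal reading | Long cycle length read first, then short | None |

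**2. Order of mapping in the AcQMap subgroup (Section 7.7)**

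- Presents in sinus rhythm: the paced map precedes AF induction, so voltage could be known when regions are labelled.
- Presents in AF, AcQMap paragraph: AF mapping comes first, so regions are flagged before a paced map exists. Knowledge may then run the other way, because flagged regions are known during HD grid mapping.
- Presents in AF, all-patients paragraph: cardioversion and the paced map come first.

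The last two cannot both apply. The flow chart in Appendix A, to which Section 7.7 refers, was not visible in the text reviewed. If it settles the order, the two paragraphs still need to match it.

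**3. Illustration of sensitivity (assumed inputs, not estimates for this study)**

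From the plan: 10 patients x 300 points = 3,000 points, and 30 x 300 = 9,000. Section 9.1 names a chi-square test of two proportions for the cycle-length comparison. It names no test for the region comparison, so the same test is used here, two-sided at 5%.

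Assumed: flagged regions hold 20% of points (n1 = 600, n2 = 2,400), 10% of signals elsewhere are labelled abnormal, there is no true difference, and labelling is shifted by s in flagged regions.

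Rejection probability (upper tail) = Phi[(s - 1.96 x SE0) / SE1], where SE0 uses the pooled proportion and SE1 the separate ones.

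For s = 0.05:
- SE0 = sqrt(0.11 x 0.89 x (1/600 + 1/2,400)) = 0.0143
- SE1 = sqrt(0.15 x 0.85/600 + 0.10 x 0.90/2,400) = 0.0158
- (0.05 - 0.0280)/0.0158 = 1.39, so about 92%

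| Labelling shift | Rejection, 3,000 points as independent |
|---|---|
| 2 points | 31% |
| 3 points | 57% |
| 5 points | 92% |

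With flagged share 10 to 30% and base rate 5 to 20%, a 5-point shift gives 53% to 99.7%.

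Clustering, as a simple deflation: design effect = 1 + 299 x ICC, which is 3.99 at ICC 0.01 and 15.95 at ICC 0.05. The 5-point shift then gives about 43% and 16%. This is rough, because flagged and unflagged points lie in the same patients. Clustering lowers the rejection rate, but the estimated difference is still wrong by the full 5 points.

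Long against short cycle length, 9,000 signals each, 10% base rate, treated as independent: a shift of 1 point gives 59%, and 2 points 99%.

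**The case against.** The strongest reply is that much of the measurement is objective. Voltage is a recorded value, AcQTrack contributes to region labelling, and the abnormal-electrogram rule is numeric. The study is exploratory, and some live labelling is unavoidable because contact recordings must be aimed at regions found during the procedure. All of this stands. It narrows the room for judgement without closing it: the plan does not say how the two sources of region labels combine, how deflections are counted, or what the fractionation scale is.

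Three stronger readings are tempting, and the documents do not support them.

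- A reader might infer that the labellers see the voltage map or bracket. No passage says so. Section 9.3 describes classifying each signal and then summarising by amplitude, which fits bracketing at the summary stage. Under the AcQMap paragraph of Section 7.7, patients presenting in AF have regions flagged before a paced map exists. The subgroup has persistent AF, so this may be common.
- A reader might take "This is a non-blinded comparison study" in Section 5 as an admission on this point. It closes the paragraph on the 20-patient catheter comparison and does not describe the AcQMap subgroup or electrogram reading.
- A reader might size the bias. If 20% of points are low voltage and 10 to 20% of the labelled area is picked for low voltage, then 0.9 x 0.20 + 0.1 = 28% and 0.8 x 0.20 + 0.2 = 36%. Both inputs are assumed, and the mechanism reaches only patients whose paced map came first. If that is half of them, the result is 24 to 28%.

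**Conclusion.** The gap is real and should be closed. Masking is not specified for AcQMap region labelling, fractionation grading or normal/abnormal classification, and these labels enter the comparisons that test the hypothesis. Knowledge of cycle length follows from the reading sequence described, and knowledge of region from the way contact recordings are aimed. Knowledge of voltage is possible only where the paced map comes first. The likely direction is towards the hypothesis.

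The size of the bias cannot be derived from the documents. The rejection rates above show only that small labelling shifts matter with this many points. They rest on assumed shares, base rates and shifts. The exploratory status lowers the stakes but does not remove the bias. The two mapping orders for patients presenting in AF are a separate inconsistency that must be reconciled.

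**What to change.** 1. **Region labels.** For the analysis, save and lock the labels with a time stamp before they are linked to HD grid voltage. Where the paced map was made first, re-read the stored AF recordings offline without the voltage overlay. Live labels still guide contact recording. Report AcQTrack-only regions as a sensitivity analysis where the software provides them. They should not be made the primary definition, because nothing in the plan shows that the software alone yields all four pattern types.
2. **Electrograms.** Export signals cropped to the local activation window, in random order, without cycle-length, voltage or region labels. The same analyst applies the numeric rule and a fixed, written fractionation scale, and the labels are linked back only afterwards.
3. **Text.** State who reads and whether deflections are counted by software or by hand. Reconcile the two paragraphs of Section 7.7 on mapping order.

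Cost: modest data-handling time on data that Section 10.2 already exports to separate workstations. No extra reader, patient or procedure time is needed. Limits: short-coupled beats may remain recognisable. The text describes AF contact recordings at flagged regions only, so masking there hides the pattern type but not the fact of being flagged.

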10. DATA MANAGEMENT

10.1. Access to Data

Direct access will be granted to authorised representatives from the Sponsor and host institution for monitoring and/or audit of the study to ensure compliance with regulations.

10.2. Data Recording and Record Keeping

The participants will be identified by a unique trial specific number and/or code in any database. The name and any other identifying detail will NOT be included in any trial data electronic file. A paper form assigning patient details to study codes will be kept in the study master file only.

Electroanatomical mapping data forms the majority of study data collected. Participants will be identified by their unique trial number on any data exported from the catheter laboratory computers. All clinical procedure data will be stored on secure trust servers in a password-protected folder in line with standard practice for all such clinical procedures. AcQMap data is stored on a designated ACUTUS workstation on which all clinical cases are stored. Study data for analysis will be exported at the time of the procedure in an anonymised form identifiable by study code onto separate computer workstations to allow analysis of the mapping data. Analysis work is done within the research office using these designated systems, which are password protected and accessible by the study team only.

Analysis results will then be recorded using a purpose designed Excel database.

Data will be retained for 5 years after the end of the study.

11. QUALITY ASSURANCE PROCEDURES

The study may be monitored, or audited in accordance with the current approved protocol, GCP, relevant regulations and standard operating procedures.

12. ETHICAL AND REGULATORY CONSIDERATIONS

12.1. Declaration of Helsinki

The Investigator will ensure that this study is conducted in accordance with the principles of the Declaration of Helsinki.

12.2. Guidelines for Good Clinical Practice

Clinical Research Protocol Template version 12.0

CONFIDENTIAL

The Investigator will ensure that this study is conducted in accordance with relevant regulations and with Good Clinical Practice.

12.3. Approvals

The protocol, informed consent form, participant information sheet and any proposed advertising material will be submitted to an appropriate Research Ethics Committee (REC), and HRA for written approval.

The Investigator will submit and, where necessary, obtain approval from the above parties for all substantial amendments to the original approved documents.

12.4. Reporting

The CI shall submit once a year throughout the study, or on request, an Annual Progress report to the REC Committee, HRA (where required) host organisation and Sponsor. In addition, an End of Study notification and final report will be submitted to the same parties.

12.5. Participant Confidentiality

The trial staff will ensure that the participants' anonymity is maintained. The participants will be identified only by a participant ID number on all trial documents and any electronic database, with the exception of the CRF, where participant initials may be added. All documents will be stored securely and only accessible by trial staff and authorised personnel. The trial will comply with the Data Protection Act, which requires data to be anonymised as soon as it is practical to do so.

12.1. Expenses and Benefits

Reasonable travel expenses for any visits additional to normal care will be reimbursed on production of receipts, or a mileage allowance provided as appropriate.

12.2. Cardiac MRI

MRI is a safe and non-invasive technique with no known risk when appropriately supervised. It does not involve ionizing radiation (X-rays). Potential participants with ferromagnetic objects in their bodies or with implanted devices which can be damaged by the CMR magnet will be excluded by carefully screening all participants for ferromagnetic objects, metal implants and other metal (e.g. shrapnel injury) every time prior to entering the scanner environment. OCMR is fully equipped for resuscitation (including defibrillation) in the unlikely event of a medical emergency during scanning. Either Advanced-Life-Support trained clinicians or Intermediate-Life-Support trained radiographers will be performing MRI scans in study participants.

While most people do not experience discomfort in a MRI environment, the enclosed space of the scanner can potentially feel uncomfortable. Discomfort from lying still for a long period of time will be minimized with comfortable padding and positioning. People with a history of claustrophobia would be excluded from participation in the study. Participants will be given a chance to see the scanner before the study starts. Whilst in the scanner, participants are able to use the alarm button or can squeeze a bulb placed in their hands if they wish to communicate with the operator or to interrupt the scanning at any stage of the scanning process. As the MRI scanner is noisy, participants would be fitted with ear-

plugs and/or acoustically shielded headphones to minimize the noise and aid communication between participants and investigators.

Once contraindications to magnetic resonance imaging are excluded by use of the facility's screening forms, the risks of undergoing a scan are minimal. A trained scanner operator or radiographer will go through a list of possible risks with the participant before scanning. The MRI scanner consists of a large powerful magnet. Magnetic resonance imaging uses no ionizing radiation. There are, however, potential hazards associated with MRI and the scanning of participants including the presence of surgical implants, participants' clothing, jewellery (such as body piercings) bodily habitus, or medical conditions. A comprehensive list of potential risks has been compiled, and the participant should be checked against this by the operator, prior to entering the controlled areas of the MRI scanners. Participants will be asked to wear a gown for the CMR scans that preserves their modesty while remaining loose in the scanner to avoid potential burns from synthetic clothing. To help maintain participant dignity they will be asked to leave their underwear on, so long as it is not made of synthetic material and has no metal parts (e.g. zips, bras clasps or studs). Participants will be asked to change in a changing room near to the scanner and will be given a locker to securely store their belongings. If they are unable to change into the gown by themselves a member of staff will be on hand to aid.

Gadolinium contrast is widely used for clinical indications in CMR and is safe. Occasionally it may cause a mild headache, nausea, itching and very rarely (< 1 in 5000) a more severe allergic reaction. It is cleared within hours by the body. Gadolinium has recently been associated with nephrogenic systemic fibrosis in patients with severe renal dysfunction; hence, as per departmental guidelines, based on Food and Drug Administration guidelines, all patients with glomerular filtration rate (GFR) < 30 ml/min (stage 3-5 renal disease) should not be given gadolinium. For this study, all potential participants with a GFR < 30 ml/min will be excluded (see Exclusion Criteria). It is known that small amounts of gadolinium deposits can remain in the body, including the skin, bones and the brain. There has been no scientific evidence todate that these gadolinium deposits are harmful or lead to adverse health effects, although this is an active area of research.

The current study is wholly research-oriented, and the images of the heart are for specific research purposes only, and are not suitable for diagnostic opinions. However, although the images are not diagnostic scans, in the event of an abnormality of clear clinical relevance being noted incidentally, a designated clinical specialist would discuss the implications with the patient and arrange for further investigations as necessary.

